## 4.2 Protocol Deviations

In the event the Nu-V3 device is inadvertently removed or the device comes off, the participant will contact the Principal Investigator. The Principal Investigator will determine the appropriate course of action to be taken.

If the study participant is unable to wear the device on their left ear, the study participant will be allowed to wear the device on their right ear, which will result in a minor study deviation. Left-ear deviations could be due to discomfort, sleep position, pain at the local site, or infection. A lack of significant improvement by the end of week 4, per the Principal Investigator's discretion, can also result in a deviation from left-ear placement.

Device placement should be recorded on the study treatment form within the electronic data capture system.

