- Participants with any changes to Pain/Anxiety/Depression/Sleeplessness medications within last 60 days (participants that do not meet this medication change washout period may be delayed until 60-day period is met)
- Participants that are currently under adjudication process for disability support, VA or other

Accountability: Patients were exited from the study upon completing the final protocol-required questionnaires. In some cases, patients prematurely exited or withdrew from the study for the following reasons, including but not limited to:

- Not eligible for treatment (including patients who may have signed informed consent and been enrolled).
- Patient experienced a SAE or UPIRTSO.
- Voluntary withdrawal- the patient voluntarily chose not to participate further in the study.

- Lost to follow-up (LTFU) – the patient was more than 10 days late to a study visit and three documented attempts to contact the patient were unsuccessful. A patient who missed a study visit but attended subsequent visit (if required) was no longer considered lost to follow-up. A missed visit was considered a protocol deviation and the deviation was documented and reported.
- Physician decision – in the physician’s opinion, it was not in the best interest of the patient to continue study participation.

The tables below summarize patients who exited the study early, as well as those who completed all study participation as per protocol.

Table 1: Study Exit Summary- Early Exit (<8 weeks)			
	Phase I	Phase II	Total Enrolled
Voluntary Withdrawal			
Lost to Follow-Up			
Physician’s Decision			
SAE / UPIRTSO			
Other			
Overall “exited” Patients			

Table 2: Study Exit Summary (≥ 8 weeks)			
	Phase I	Phase II	Total Enrolled
Completion of Study as Planned			
Voluntary Withdrawal			
Lost to Follow-Up			
Physician’s Decision			
SAE / UPIRTSO			
Other			
Overall “exited” Patients			

Insert Study Exit Analysis Here

Section 1.0: Participant Flow

ClinicalTrials.gov

A service of the National Institutes of Health

Edited: 19 August 2014

Participant Flow Data Preparation Checklist

Overview: A tabular summary of the participants' progression through each stage of a study by group. Use this checklist with the [Participant Flow Template](#)^Δ and [Results Data Element Definitions](#).

	Information to have available for Participant Flow	Term

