	
 For each Period, the number of participants in each group that: 
 Started—Generally, the participants assigned (or randomized) to each group 
 Additional Milestone (optional)—Any important event(s) during study Completed—As defined for the study Tip: If the number of participants starting the first Period is different from the total enrolled in the study, explain why in Pre-assignment Details 	
 ^{*Δ}Started ^{*Δ}Completed
	
 For each Period, the number of participants in each group that dropped out and the reasons they dropped out 	^Δ Reason(s) Not Completed

^{*}Required
^ΔTemplate Field

Figure 1.1- Participant Flow Checklist

NU-V3 CONSORT 2010 FLOW DIAGRAM

[figure not shown]

Figure 1.2- Participant Flow Diagram

Participant Flow Template		Nu-Life Solutions
Recruitment Details		
[*] Pre-assignment Details		
Period		
Phase I		Initial Clinical Study 50 - 100 participants
*Arm/Group Title		
*Arm/Group Description		
		Number of Participants
*Started		
[*] Milestone Title		
[*] Milestone Title		
[*] Milestone Title		
*Completed		
Not Completed		(automatically calculated)
Reason Not Completed		
[*] Voluntary Withdrawal		
[*] Lost to Follow-Up (LTFU)		
[*] Physician's Decision		
[*] SAE/ UPIRTSO		
[*] Protocol Violation		
[*] Other		
Phase II		Expanded Clinical Study 100-200 participants
*Arm/Group Title		
*Arm/Group Description		
		Number of Participants
*Started		
[*] Milestone Title		
[*] Milestone Title		
[*] Milestone Title		
*Completed		
Not Completed		(automatically calculated)
Reason Not Completed		
[*] Voluntary Withdrawal		
[*] Lost to Follow-Up (LTFU)		
[*] Physician's Decision		
[*] SAE/ UPIRTSO		
[*] Protocol Violation		
[*] Other		

*required

[*] conditionally required

Figure 1.3- Participant Flow Template

Insert Data Collection Summary Here

Section 2.0: Baseline Characteristics

Demographics: The total population consisted of _____ patients. Information on the enrolled patients (n=) patients is provided in the following tables.

A service of the National Institutes of Health

Edited: 19 August 2014

Baseline Characteristics Data Preparation Checklist

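### The planned exit categories have no place for device discomfort, non-serious adverse events or lack of benefit, so the exit tables will not show how many patients left because of the device

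*SAP*

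**What the plan says.** The Accountability section of the SAP gives five reasons for leaving early: ineligibility, an SAE or UPIRTSO, voluntary withdrawal, loss to follow-up and physician decision. The harm-related reason reads "Patient experienced a SAE or UPIRTSO". Voluntary withdrawal is "Voluntary withdrawal- the patient voluntarily chose not to participate further in the study". Physician decision applies when, in the physician's opinion, "it was not in the best interest of the patient to continue study participation". The list is explicitly open; patients may have "prematurely exited or withdrew from the study for the following reasons, including but not limited to" those named.

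Table 1 (exit before 8 weeks) and Table 2 (8 weeks or later) have rows for Voluntary Withdrawal, Lost to Follow-Up, Physician's Decision, SAE / UPIRTSO and Other. Table 2 also has a completion row. The Participant Flow template (Figure 1.3) repeats the exit rows and adds "Protocol Violation". The analysis of exits is a placeholder: "Insert Study Exit Analysis Here".

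In the protocol, Section 8.1 and the SAP's primary endpoints limit the primary safety endpoint to UPIRTSOs. Section 4.2 foresees trouble with wearing the device: "Left-ear deviations could be due to discomfort, sleep position, pain at the local site, or infection". It also names lack of significant improvement by the end of week 4. Both are given there as reasons for departing from left-ear placement, not for leaving the study.

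**The concern.** A patient who gives up because the pads hurt, or because nothing improved, has chosen to stop and so meets the definition of voluntary withdrawal. So does a patient who moves house. If the investigator acts first, the same exit can become Physician's Decision, and Other is undefined. Whichever row is used, the reason disappears.

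Two things are at stake. The first is tolerability. The trial is single-arm and open-label, its primary safety endpoint counts only UPIRTSOs, and the SAP calls it the primary pivotal study for the De Novo request. With no control arm to compare exit rates against, the stated reason for leaving is one of the few direct signs of whether people can live with the device. The second is the Week 8 result. The SAP states imputation for the safety endpoint and none for effectiveness. If the Week 8 medians are taken over patients still reporting, those who left for discomfort or no benefit drop out of them, and probably not at random.

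**Working it through.** There is no stated figure to reproduce, since the documents give no exit rate and no expected median or SD. The check is a comparison of the category lists and forms, followed by one illustration.

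**Step 1: the three lists side by side.**

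| Reason | Accountability list | Tables 1 and 2 | Figure 1.3 |
|---|---|---|---|
| Not eligible | yes | no | no |
| SAE / UPIRTSO | yes | yes | yes |
| Voluntary withdrawal | yes | yes | yes |
| Lost to follow-up | yes | yes | yes |
| Physician's decision | yes | yes | yes |
| Protocol violation | no | no | yes |
| Other | open wording only | yes | yes |
| Device discomfort or non-serious adverse event | no | no | no |
| Lack of benefit | no | no | no |

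The last two rows are the point. The first row and the protocol-violation row are a smaller mismatch: "Not eligible for treatment (including patients who may have signed informed consent and been enrolled") is a listed reason with no row in any table, and protocol violation is a row with no counterpart in the list.

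**Step 2: could another form supply the reason?**

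- Weekly Treatment Form (Appendix 9), as shown: serial number and ear used. No exit field.
- PTB-7 (Appendix 11): perceived benefit 0-100%, comfort, and major discomfort that required adjusting placement. It describes patients while they report and does not ask why they stop.
- Unanticipated Problem Form (Appendix 7): relationship to the device and action taken, including discontinuation, but only for events reported on it.

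So no form shown asks for the reason for exit, although the SAP's own Participant Flow checklist (Figure 1.1) asks for dropout reasons.

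**Step 3: what the tables could conceal (assumed rates).** If 10-20% withdraw voluntarily, that is 5-10 of 50 patients or 10-20 of 100. The number leaving because of the device could be anywhere from none to all of them, and the tables would look the same.

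**Step 4: possible effect on a Week 8 median (all inputs assumed).** Take 100 patients, of whom d leave early. Let change in stayers be normal with median -3 and SD 4, negative being better. If leavers get the worst rank, the overall median is the stayers' quantile at 50/(100 - d):

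median = -3 + 4 × z(50/(100 - d))

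- d = 5: 50/95 = 0.526, median -2.74
- d = 10: 50/90 = 0.556, median -2.44
- d = 15: 50/85 = 0.588, median -2.11

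At d = 10 the shift is 0.56, or 0.56/4 = 0.14 of the assumed SD. The direction of the result does not change. The formula depends only on the fraction leaving, so it applies equally within a symptom stratum, where the actual analysis is done.

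**The case against.** The strongest reply is that the plan leaves more room than the missing rows suggest. Much of it stands.

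- A reader might infer that the SAP assigns these patients to Voluntary Withdrawal. It does not. The list is open, and Physician's Decision and Other could also take them. But that only spreads such exits over more unlabelled rows.
- A reader might infer that the trial has no means of reporting device-related exits. That is too strong. Protocol Section 7 has the Unanticipated Problem Form cover problems that are unforeseen or involve risk. The form allows CTCAE Grade 1 and records device relationship and discontinuation. PTB-7 answers before exit give a partial, indirect signal. Foreseen discomfort and lack of benefit, however, need not reach the form, and PTB-7 does not link to the decision to leave.
- A reader might infer that these patients cannot be treated as failures unless the reason is recorded. That is wrong. Worst rank can be given to every early exit from exit status alone, and this is at least as conservative as a reason-specific version.
- Protocol Section 4.2 concerns which ear is used. It shows that discomfort and non-response were foreseen, not that they were expected to cause exits.
- The documents do not state that the Week 8 analysis uses completers only; the analysis population fields are blank. That is a separate gap.
- The SAP is a partly empty shell, the CONSORT diagram is not shown and some pages are not available, so an exit reason recorded elsewhere cannot be ruled out.

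**Conclusion.** The point holds in a limited form. As the categories stand, exits for device discomfort, a non-serious adverse event or lack of benefit have no row of their own, so Tables 1 and 2 and Figure 1.3 will not show how many patients left because of the device. Exits through an SAE or UPIRTSO will be counted.

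The size cannot be derived from the documents. The shift from -3.0 to -2.4 (range -2.7 to -2.1 for 5 to 15 exits per 100) is purely illustrative. It rests on an assumed exit rate, median, SD and normal shape, and on no patient who leaves doing better than worst rank.

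The mismatch between the lists is housekeeping. The whole is a cheap improvement of low severity. Its main claim to attention is timing, because reasons for leaving cannot be reconstructed reliably after the patient has gone.

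**What to change.** 1. Add one question at every early exit recording the primary reason.
2. Use one common list in the Accountability section, Tables 1 and 2 and Figure 1.3. Split Voluntary Withdrawal and Physician's Decision each into device discomfort or non-serious adverse event, lack of benefit, and other or unrelated. Give Not Eligible and Protocol Violation a row in all three places.
3. Report device-related exits in the SAP's safety section beside the UPIRTSO counts.
4. Add one Week 8 sensitivity analysis within each symptom stratum in which all early exits receive the worst rank. The median stays estimable while exits are under half of the stratum. As a refinement, repeat it with worst rank only for exits due to discomfort or lack of benefit.

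The cost is one question, a few table rows and one sensitivity run with a variant. The drawbacks are that self-stated reasons are imperfect, cells will be small in a study of 50-100 patients split by symptom, and tolerability and effect may look slightly less favourable.

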Primary Endpoints: Primary endpoints consisted of the following:

1. **Safety:** The primary safety endpoint was the occurrence of reported unanticipated problems involving risk to subjects or others (“UPIRTSOs”). These UPIRTSOs are defined as those problems which alter the risks to subjects or others. This includes any study suspensions or holds. The primary safety endpoint analyses were based on a risk-benefit conclusion.
2. **Effectiveness:** The primary effectiveness endpoints were overall reduction in median reported symptoms of pain, anxiety, depression, and/or sleeplessness via numeric rating scales at 8 weeks. This primary effectiveness is measured by median reported symptom reductions in pain, anxiety, depression, and/or sleeplessness via the following validated tools: Pain intensity and interference- PEG Scale, Anxiety- Generalized Anxiety Disorder 7-item (GAD-7) scale, Depression- Patient Health Questionnaire (PHQ-9), Sleeplessness- PROMIS short form 4a, and overall improvement of quality of life (QOL) - Patient’s Global Impression of Change (PGIC).

The patient’s perceived treatment benefit and device comfort information, will be captured via the non-validated tool, Perceived Treatment Benefit Form (PTB-7). This effectiveness tool will measure median levels of reported perceived treatment benefit and device comfort.

The hypothesis-driven criterion of effectiveness was to show that there was a statistically significant reduction in the median reported pain, anxiety, depression, and/or sleeplessness levels of patients using the Nu-V3 device. The second criterion was intended to show that there was a statistically significant improvement in reported quality of life and perceived treatment benefit secondary to overall reported symptom reduction of pain, anxiety, depression, and/or sleeplessness.

Secondary Endpoints: Secondary endpoints consisted of the following:

1. **Effectiveness:** The secondary effectiveness endpoint was overall reduction in median reported symptoms of pain, anxiety, depression, and/or sleeplessness via numeric rating scales at 4, 8, and 12 weeks. This was measured via the following validated tools: Pain intensity and interference- PEG Scale, Anxiety- Generalized Anxiety Disorder 7-item (GAD-7) scale, Depression- Patient Health Questionnaire (PHQ-9), Sleeplessness- PROMIS short form 4a, and overall improvement of quality of life- Patient’s Global Impression of Change (PGIC).

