Risks to Health: Potential unanticipated problems require prompt reporting to Aspire IRB. These problems potentially place subjects or others at greater risk of physical or psychological harm than was previously recognized, and warrant consideration of substantive changes in the protocol or informed consent process or other action in order to protect the safety, welfare, or rights of participants. Aspire IRB must be notified within 5 calendar days of the event. The completed IRB Unanticipated Problem form (Appendix 3) must be received by Aspire IRB within 10 calendar days of the event. Unanticipated problems are defined as those problems which alter the risks to subjects or others. This includes any study suspensions or holds. This form will be used to report any problem that is unforeseen or involves risk. One form will be used per event or problem.

Table 4.1: Unanticipated Problems Involving Risk to Patients or Others			
	Phase I	Phase II	Total
UPIRTSO 1 (number)			
UPIRTSO 2 (number)			
UPIRTSO 3 (number)			
Overall UPIRTSOs Reported			

Table 4.2: Risk/ Mitigation Measures	
Identified Risk	Mitigation Measures

Insert Safety Analysis Here

Section 5.0: Results

Results: The principal safety and effectiveness results from patients in the Nu-V3 study are provided below. The primary safety analysis was based on all patients registered and included all reported UPIRTSO events. The primary safety endpoint included imputation for missing clinical outcomes data using the logistic regression method. The imputation model included baseline characteristics including age, sex/gender, marital status, primary language spoken, race/ethnicity, education history, and veteran status.

Primary Safety Endpoint:

Insert Primary Safety Endpoint Statistical Analysis

Insert Primary Safety Endpoint Statistical Table

Primary Effectiveness Endpoint:

Insert Primary Effectiveness Endpoint Statistical Analysis

Insert Primary Effectiveness Endpoint Statistical Table- 8 weeks

Secondary Effectiveness Endpoint:

Insert Primary Effectiveness Endpoint Statistical Analysis

Insert Primary Effectiveness Endpoint Statistical Table: 4, 8, 12 weeks

Sub-Analyses:

Insert Sub-Analyses Statistical Analysis

Insert Sub-Analyses Statistical Tables

Special Controls:

Insert Special Control Section Here

Benefit/Risk Determination:

Insert Benefit/Risk Section Here

Section 5.0: Administrative Information

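### The SAP imputes missing outcomes for the primary safety endpoint by logistic regression, but that endpoint counts reported events, has no defined missing value per patient, and will probably be too sparse for the model.

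*SAP*

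**What the plan says.** The SAP, under Primary Endpoints, defines safety this way: "The primary safety endpoint was the occurrence of reported unanticipated problems involving risk to subjects or others". It adds: "These UPIRTSOs are defined as those problems which alter the risks to subjects or others. This includes any study suspensions or holds". On how the endpoint is judged it says only: "The primary safety endpoint analyses were based on a risk-benefit conclusion". Protocol Section 8.1 agrees. SAP Section 4.0 (Risks to Health) asks for one form per event or problem, so the reporting unit is the event and not the patient.

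SAP Section 5.0 (Results) sets the population: "The primary safety analysis was based on all patients registered and included all reported UPIRTSO events". It then brings in the imputation, "The primary safety endpoint included imputation for missing clinical outcomes data using the logistic regression method", and describes the model: "The imputation model included baseline characteristics including age, sex/gender, marital status, primary language spoken, race/ethnicity, education history, and veteran status".

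Nothing further is given. The safety analysis and its table are insert-here placeholders. Neither document names:

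- the estimator, or whether imputation is single or multiple;
- the coding of the factors;
- a rule for few or zero events;
- the circumstances in which a patient's UPIRTSO status counts as missing.

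Table 4.1 does keep a row of observed counts, "Overall UPIRTSOs Reported".

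**The concern.** A logistic imputation model needs a yes/no outcome for each patient, some patients whose outcome is known to be unobserved, and enough events to estimate its coefficients. The endpoint as defined supplies neither of the first two, and the third is doubtful at this sample size.

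What is at stake is the meaning of the primary safety figure. If status is declared missing for some patients, their contribution to the figure would come from an estimator that nobody has named. It would also come from predictors such as marital status and primary language, which have no stated link to device harm. The choice could be made after the data are seen. The SAP describes this as the primary pivotal study behind the De Novo request, so the safety summary should rest on what was reported, with its uncertainty visible.

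**Working it through.** The plan states no event rate, missing rate, precision or power for safety, so there is no figure to reproduce.

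**1. Endpoint against method.**

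| The model needs | The endpoint supplies |
|---|---|
| One binary outcome per patient | Events, one form each |
| A defined missing value | Reported problems; absence of a report reads as no event |
| A patient row for each outcome | Also study holds and problems affecting others, which have no patient row |

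This part needs no assumption about rates.

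**2. Size of the model.** The SAP Section 2.0 baseline templates list age in 7 levels, sex 4, marital status 4, language 13, race/ethnicity 9, education 11 and veteran status 3. If each level became a model term:

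terms = sum of (levels - 1) = 6 + 3 + 3 + 12 + 8 + 10 + 2 = 44, or 45 parameters with the intercept.

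The education table prints 10 rows against 11 in its own heading, which would give 43. The smallest coding is one term per factor: 7 terms, 8 parameters. Planned sizes are 50-100 (Phase I), 100-200 (Phase II) and 150-300 (total).

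**3. Events available.** Expected events = N x p, and P(no event) = (1 - p)^N. The rates are assumed.

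| N | p = 1%: expected, P(none) | p = 5%: expected, P(none) |
|---|---|---|
| 50 | 0.5, 60.5% | 2.5, 7.7% |
| 100 | 1, 36.6% | 5, 0.6% |
| 300 | 3, 4.9% | 15, about 0% |

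Even at 10% with N = 300 there would be 30 events against 45 parameters.

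**4. Whether a finite maximum-likelihood fit exists.** Separation was tested by linear programming, with empty levels dropped, in 200 simulated data sets per setting at N = 50, 100 and 300. The category mixes are assumed. Share with no finite fit:

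| Coding | 1-3 events | 5 events | 10 events |
|---|---|---|---|
| SAP categories | 100% | 100% | 100% |
| 7 binary terms, skewed mix | 97-100% | 84-85% | 43-45% |
| 7 binary terms, balanced mix | 87-100% | 33-38% | 1-2% |

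At zero events no finite fit exists under any coding. A fresh run with a different assumed mix again gave 100% for SAP categories at 1, 2, 3, 5 and 10 events. For balanced binary terms it gave 86-100% at 1-3 events, 32-37% at 5 and 1-2.5% at 10.

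**5. What a direct summary looks like.** Exact (Clopper-Pearson) 95% intervals for two assumed cases with 50 registered patients, all fitted with a device:

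| Case | All registered | Event or complete follow-up | Bound |
|---|---|---|---|
| 1 event, 10 incomplete | 1/50 = 2.0% (0.05-10.6%) | 1/40 = 2.5% (0.06-13.2%) | (1 + 10)/50 = 22% |
| 0 events, 5 incomplete | 0/50 = 0% (0-7.1%) | 0/45 = 0% (0-7.9%) | (0 + 5)/50 = 10% |

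Dividing by all registered patients silently counts unknowns as non-events and narrows the interval, so both denominators are needed.

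**The case against.** The best case for leaving the text alone has four parts.

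- **No finite fit is not the same as no imputation.** Fitted probabilities can still be computed under separation, and penalised or prior-based estimators always return an answer. Plugging in maximum-likelihood probabilities would give roughly the complete-case rate, and 0% when no event is observed. This stands. A reader might infer from the 100% failure rate that the reported safety rate would be badly wrong, and the documents do not support that. In simulations with 0 events in 45 patients and 5 missing, completed rates ran from 0% to 3.4% by estimator with SAP categories. For pooled data with 3 events in 270, 30 missing and seven terms, they ran only from 1.1% to 1.5%. Those ranges rest on assumed inputs, and the conclusion does not depend on them.
- **The 44-term model is not the SAP's.** The templates are for reporting, they offer customized rows, and the predictor list is open. This also stands; 44 terms is one possible reading. The seven-term results show that coarse coding still fails at 1-3 events.
- **The SAP never says that holds would be imputed.** That is correct, and a hold is hardly a clinical outcome. But the sentence attaches imputation to the endpoint as a whole, and the endpoint includes holds.
- **Little turns on it.** There is no test or threshold, the judgement is qualitative, observed counts remain, and the SAP is openly a shell. This limits the severity. It does not remove the point, because here the SAP is not silent: it states a specific rule that does not suit its endpoint.

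**Conclusion.** The concern holds in a limited form and should be fixed. The mismatch between a reported-event endpoint and a patient-level imputation model follows from the text alone. The estimation problem depends on assumed event counts, coding and category mix. Within those assumptions it is near certain with the SAP's categories, usual at 1-3 events with seven binary terms, and much reduced by about 10 events. It matters most at Phase I size and least for pooled data with coarse coding.

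The documents do not show that the safety conclusion would be wrong, that reported events would be lost, or that any formal decision depends on the imputed value. What they do show is a primary safety figure that could not be reproduced from the plan as soon as any status is declared missing.

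**What to change.** Delete the two imputation sentences in SAP Section 5.0 (Results) and replace them with:

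> The primary safety analysis lists all reported UPIRTSOs, including suspensions or holds and problems affecting others, by phase, in total and by study period. For the treatment period (device placement to the end of the 8-week treatment) it reports the number and percentage of patients with at least one patient-level UPIRTSO, with exact (Clopper-Pearson) 95% CI, (i) among all registered patients, stating that those with incomplete follow-up are counted as having no reported event, and (ii) among patients with a reported event or complete treatment-period follow-up. No UPIRTSO is imputed by model. As a sensitivity bound for the same period, patients with at least one device placed, no reported UPIRTSO and follow-up ending before the end of treatment are counted as events; patients never fitted with a device are not.

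Three details matter:

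- **Same window throughout.** The percentage and the bound must cover the same period, or the bound does not bound it. The period should be defined by elapsed treatment and not by the Week 8 visit, because the assessment table still shows a pad replacement at that visit.
- **Never-fitted patients.** SAP Accountability allows enrolled patients to exit as ineligible. Counting them as device events would make no sense.
- **No new data.** The SAP already separates exits before 8 weeks, in "Table 1: Study Exit Summary- Early Exit (<8 weeks").

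The cost is SAP wording only. The downsides are that events after loss to follow-up are not adjusted for by a model, that denominator (ii) leans high because incomplete patients enter it only if they had an event, and that the bound will be wide if many patients exit early.

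Separately, the post-treatment observation period is 4 weeks in Protocol Section 4.0 and 2 weeks in the SAP Design text for both phases. Those passages must be reconciled before this analysis is extended past treatment.
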